4. CHANGES IN THE PLANNED ANALYSIS OF THE STUDY

1. In the random coefficient model used to estimate slope in change from baseline of eGFR (CKD-EPI)_{cr}, an additional fixed effect term of interaction of eGFR (CKD-EPI)_{cr} at baseline (continuous) by time is included.
2. As per protocol the objective of the trial is “to demonstrate superiority of empagliflozin 10 mg versus placebo”.
The ITT analysis approach was chosen to as closely as possible reflect real-life conditions, disregarding any occurrences of treatment stop or restart of treatment, that may happen in clinical practice as well.
However, it is also recognized and recommended by the Executive Steering Committee that the study-specific treatment discontinuation in the close-out period does not resemble clinical practice.
Therefore for patients that complete the treatment period according to protocol after close-out announcement the time at risk for efficacy endpoints ends at the discontinuation of treatment and events occurring thereafter are not considered in the efficacy analyses.
The primary estimand is now specified in [Section 7.4](#).
An analysis including all events after randomization will be conducted as sensitivity analysis for the primary endpoint and the key secondary endpoint of recurrent HHF. A corresponding approach will be used for continuous endpoints.
3. Mixed model for repeated measures (MMRM) for KCCQ at week 52 as well as other MMRMs were specified in condensed form to be in line with BI internal standards. Therefore, individual model terms were removed from the MMRM if already included as interaction term with treatment or visit. Additionally, the terms included in MMRMs were aligned throughout the TSAP
4. The rules defining ‘win’ and ‘lose’ for the win ratio calculation were clarified and adapted to also consider the time to first HHF event in case of a tie in the number of HHF events. The adaption was made since time to first HHF event is also considered relevant information to avoid ties in case the number of HHF events is identical. This approach is a modification of the rules applied by Rogers 2014 ([8](#)).

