1. Time to first event of adjudicated CV death or adjudicated HHF
2. Occurrence of adjudicated HHF (first and recurrent)
3. eGFR (CKD-EPI)_{cr} slope of change from baseline

Starting from step 1, if the null hypothesis of no difference is rejected, and the result is more favourable for empagliflozin, superiority is concluded in the tested endpoint, and the overall type I error is preserved for the test in the next step. If at any step the null hypothesis of no difference is not rejected, subsequent tests are conducted in an exploratory manner.

The overall type I error rate will be preserved at a level of 0.05 (2-sided). The type I error rate used at the final analysis will be influenced by the pre-planned interim analysis.

In the final analysis after the evaluation of recurrent HHF, alpha will be split into 0.001 to be used for the analysis of eGFR slope, and the rest will be transferred to the meta-analyses.

In case the trial is finished early at the time of interim analysis, using $\alpha_{interim}$ for the primary and key secondary endpoints in the testing hierarchy according to the α -spending function above, the following α -split will be used for the eGFR slope analysis and the meta-analysis:

0.1 * $\alpha_{interim}$ will be used for the eGFR slope analysis and

0.9 * $\alpha_{interim}$ will be transferred to the meta-analyses

In both the interim and final analyses, if the slope analysis is successful, the alpha of this branch will then be transferred to the meta-analyses.

The testing hierarchy is summarized in Figure 7.4.1: 1.

[figure not shown]

Figure 7.4.1: 1 Hierarchical analysis of trial in HFpEF (1245.110) and the parallel trial in HFrEF (1245.121) showing the alpha-spending at the final analysis

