The number of HHF events per patient will be summarized descriptively. Additionally a negative binomial model will be fitted to the data of recurrent HHF. This will be done once including only treatment as covariate and once including all covariates as the primary model. Rate ratio and confidence intervals of both models will be reported.

The mean cumulative incidence will be displayed for adjudicated recurrent HHF.

Subgroup analyses will be explored as outlined in [Section 6.4](#) for adjudicated recurrent HHF. For subgroup analyses the term of subgroup (if not already part of the model) and subgroup by treatment will be added to the model of the recurrent event. If the subgroup variable is a categorization of a continuous covariate, this covariate will be dropped from the subgroup model.

eGFR (CKD-EPI)_{cr} slope of change from baseline

Slope in change from baseline of eGFR (CKD-EPI)_{cr} will be analysed by a random coefficient model allowing for random intercept and random slope per patient. The model will include the factors treatment, sex, geographical region, and status of DM as fixed effects and eGFR (CKD-EPI)_{cr} at baseline (continuous), LVEF (continuous), age (continuous), time and interaction of treatment by time and interaction of eGFR (CKD-EPI)_{cr} at baseline

(continuous) by time as linear covariates and allow for randomly varying slope and intercept between patients. The model will include all on-treatment change from baseline data.

Since the slope is run on the change from baseline data, the intercept will model the acute drop, whereas the long-term effect is modelled by the slope.

A plot of individual patient slopes and separately of individual patient intercepts will be provided per treatment and by eGFR at baseline.

Subgroup analyses as outlined in [Section 6.4](#) will be explored for eGFR slope. The subgroup model will include additionally to the model described above, the subgroup if not already part of the model, subgroup by treatment and subgroup by treatment by time. If the subgroup variable is a categorization of a continuous covariate, this covariate will be dropped from the subgroup model.

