9.3 DEFINITION OF DM AT BASELINE

Table 9.3: 1 DM at baseline

Diabetes status at baseline	Definition
T1DM	Patients who fulfil one of the following: 
- investigator-reported medical history of diabetes on the medical history page AND 
- type of diabetes is T1DM
T2DM	Patients who do not have T1DM but fulfil one of the following: 
- investigator-reported medical history of diabetes on the medical history page OR- any pre-treatment HbA1c value ≥ 6.5 OR- stratification via IRT in group of diabetes with either missing assessment of history of diabetes on the medical history page, or no pre-treatment measurement of HbA1c available and investigator reported 'no' for the medical history of diabetes

Table 9.3: 1 DM at baseline (cont.)

Diabetes status at baseline	Definition
Pre-DM	
Patient who fulfil one of the following:
 
- investigator reported ‘no’ for the medical history of diabetes on the medical history page AND no pre-treatment HbA1c ≥ 6.5 and a pre-treatment HbA1c value of ≥ 5.7 and < 6.5 
OR
 
- stratification via IRT in group of pre-diabetes with either
○ missing assessment of history of diabetes on the medical history page and no pre-treatment HbA1c ≥ 6.5 or○ no pre-treatment measurement of HbA1c and investigator reported ‘no’ for the medical history of diabetes 
OR
 
- missing assessment of history of diabetes on the medical history page AND all pre-treatment HbA1c < 6.5 and a pre-treatment HbA1c value of ≥ 5.7 and < 6.5 and stratification via IRT in group of no diabetes
Normal (excluding pre-DM)	Patients not meeting the criteria of DM or pre-DM

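### In the confirmatory eGFR slope model only baseline eGFR, among the prognostic covariates, is crossed with time; adding diabetes status and the other stratification covariates by time could only hold or modestly improve precision

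*SAP*

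**What the plan says.** The current SAP (revised 12 February 2021) specifies the slope model in Section 7.5.1. It has the "factors treatment, sex, geographical region, and status of DM as fixed effects". The linear covariates are baseline eGFR together with "LVEF (continuous), age (continuous), time and interaction of treatment by time and interaction of eGFR (CKD-EPI)_{cr} at baseline". The model is also to "allow for randomly varying slope and intercept between patients". The data are on-treatment changes from baseline, and the SAP adds that "the intercept will model the acute drop, whereas the long-term effect is modelled by the slope".

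The baseline eGFR by time term was a deliberate change. Section 4 records that "an additional fixed effect term of interaction of eGFR (CKD-EPI)_{cr} at baseline (continuous) by time is included". It gives no reason for treating this covariate differently from the rest.

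In Section 7.4.1 the slope is the third step of the confirmatory hierarchy. At the final analysis "alpha will be split into 0.001 to be used for the analysis of eGFR slope"; after an interim stop the slope gets 0.1 x alpha_interim. If the slope test succeeds, its alpha passes to the meta-analyses.

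The SAP does not list the randomisation strata. Section 7.4.1 says they are among the Cox covariates (region, diabetes, age, sex, LVEF, baseline eGFR). Table 9.3: 1 identifies diabetes status as one of them, through wording such as "stratification via IRT in group of diabetes".

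**The concern.** A covariate without a time interaction moves a patient's whole expected profile up or down and leaves the expected slope alone. The tested quantity is a difference in slopes. Apart from baseline eGFR, then, covariate adjustment does not reach it. If patients with diabetes lose eGFR faster than patients without, at the same baseline eGFR, the model treats that difference as unexplained variation between patients. The standard error of treatment by time is then larger than it need be.

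Diabetes status is the clearest case. It was a stratum, Section 6.4 calls it the most important subgroup, and the slope subgroup model in 7.5.1 includes subgroup by treatment by time. At stake is some power at a confirmatory step with a small alpha.

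**Working it through.** **The plan's own figures.** The SAP gives no effect size, slope SD, residual SD or power for the slope. Its only sizing is for the primary endpoint (9.6), and that reproduces. Schoenfeld's formula at hazard ratio 0.80, 90% power and two-sided 0.05 gives 845 events against 841. With a 10% yearly event probability, 18 months of accrual and 20 months of follow-up, N is 4125 against 4126. Neither figure bears on the slope, so the rest is an illustration under stated assumptions.

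**Inputs.**
- From the SAP: visits at weeks 4, 12, 32, 52, 76, 100, 124 and 148 (Table 6.7: 1); slope alpha 0.001 at the final analysis, read as two-sided because 7.4.1 makes all tests two-sided.
- Assumed: random-slope SD sb = 2-4 per year and residual SD se = 4-6 (mL/min/1.73 m2); follow-up spread evenly over 0.8-3.3 years with a last value at end of treatment; half the patients diabetic; starting power 80%.
- d is the slope difference between diabetic and non-diabetic patients, in mL/min/1.73 m2 per year, that remains after baseline eGFR by time.

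**Formulas.** A patient's slope has variance sb² + se²/SST, where SST is the sum of squared deviations of the visit times from their mean. The patient's weight is the reciprocal. With half the patients diabetic, diabetes by time removes 0.5 x 0.5 x d² = 0.25d² from sb². The gain in effective sample size is the sum of weights after, divided by the sum before, minus 1.

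**One patient followed for 2 years.** The visit times are 0.077, 0.230, 0.613, 0.997, 1.457, 1.916 and 2.000 years, with mean 1.041 and SST 3.63.
- sb = 2, se = 4, d = 1: before, 4 + 16/3.63 = 8.41; after, 8.41 - 0.25 = 8.16; gain 8.41/8.16 - 1 = 3.1%.
- sb = 4, se = 6, d = 1: before, 16 + 36/3.63 = 25.91; after, 25.66; gain 1.0%.

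**All patients.** Power is Φ(4.132 x √(1 + gain) - 3.291), where 3.291 is the two-sided 0.001 quantile and 4.132 = 3.291 + 0.842.

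| d | Share of slope variance, 0.25d²/sb² (sb = 4 to 2) | Gain in effective sample size | 80% power becomes |
|---|---|---|---|
| 0 | 0% | 0% | 80% |
| 0.5 | 0.4-1.6% | 0.3-0.8% | 80.1-80.5% |
| 1 | 1.6-6.3% | 1.0-3.5% | 80.6-81.9% |
| 2 | 6.3-25% | about 4-16% | 82.3-87.6% |

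**Second method.** Generalised least squares was applied to simulated data from a random intercept and slope model (residual and intercept SD 5, slope SD 2-4, follow-up 20-38 months). One composite covariate was entered first as a main effect only, then also by time. If the omitted by-time terms explain 0, 5, 10 or 20% of slope variance, the information gained on treatment by time is 0%, 2-4%, 4-7% and 9-16%. For example, at 10% and slope SD 2, the model standard error falls from 0.2105 to 0.2063, and (0.2105/0.2063)² - 1 = 4.1%. The treatment-by-time estimate showed no systematic bias under either model. With 25 simulated trials per setting, the gains are taken from the model standard errors and not from the empirical spread.

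**The case against.** The strongest reply is that this is a modelling preference. The model is prespecified and valid. Randomisation protects the treatment-by-time contrast, and unexplained slope variation goes into the random-slope variance, so the standard error reflects it. Crossing only the outcome's own baseline with time also matches the SAP's repeated-measures models (7.5.2, 7.6), which use baseline by visit and keep the other covariates as main effects. All of this stands.

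A reader might infer that the randomisation strata are not used for the slope, or that adjustment does almost nothing for it. The SAP does not support either. All six Cox covariates are in the slope model, and baseline eGFR by time does adjust the tested slope. Nor does the SAP show that LVEF, age or sex are strata.

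A reader might also take the sentence on intercept and slope as a statement about the covariates. It concerns the separation of acute from long-term change; the evidence here is the list of model terms before it.

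The gain is conditional. A material one needs d near 2. At slope SD 2, diabetes alone would then have to explain 1/4 = 25% of the slope variance left after baseline eGFR by time, and nothing in the SAP supports that. The other covariates may overlap with diabetes or add nothing. The alpha of 0.001 does not cause any loss; it only makes power at that step more sensitive to precision.

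**Conclusion.** The point holds as a free improvement and is not an error in the plan. Diabetes status, region, LVEF, age and sex cannot explain differences in the tested slope; baseline eGFR can. The loss is zero if these covariates do not predict slope. Under the stated assumptions it is about 0.3-3.5% of effective sample size for a diabetes slope difference of 0.5-1 mL/min/1.73 m2 per year, or roughly 0.1 to 2 percentage points on an assumed 80% power. It is larger only under larger assumed differences. Bias and type I error are not in question. Every slope figure here is an assumption, because the SAP gives none.

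**What to change.** Before unblinding, add status of DM by time to the slope model in 7.5.1, and likewise by-time terms for the other stratification covariates already in the model. Take the treatment-by-time coefficient from that model for the confirmatory test, at 0.001 in the final analysis and 0.1 x alpha_interim after an interim stop. Record the change in Section 4 beside the baseline eGFR by time term. If the sponsor prefers the present model, a sentence saying why only baseline eGFR is crossed with time would be enough.

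The cost is SAP wording and a few fixed-effect degrees of freedom with approximately 5750 patients planned (9.6). No new data are needed, and the estimand and type I error are unchanged.

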6.4 SUBGROUPS

Subgroups to be considered in the analyses are provided below in [Table 6.4: 1](#). Missing categories for subgroup variables will not be considered in the respective analysis.

If there is missing information for any of the subgroups, where data is also collected in the IRT system, then the information as transferred from IRT will be used to assign a patient to a certain category.

Although several subgroup analyses are prespecified in [Table 6.4: 1](#), the subgroup analysis by Diabetes at baseline (diabetic, non-diabetic) is the medically and academically most important subgroup analysis.

Table 6.4: 1 Categories of covariates for displays of baseline characteristics and subgroup analyses

Variable	Categorization	Demo-graphics ¹	Subgroups for Efficacy endpoints ²	Safety ³
Diabetes at baseline	diabetic, non-diabetic	X	X	X (except ketoacidosis and hypoglycaemia)
	non-diabetic (Pre-diabetes, normal (no pre-diabetes)), diabetic (type 2 diabetes, type 1 diabetes)	X		X (Ketoacidosis and hypoglycaemia)
Age (years)	<50 50 to <65 65 to <75 75 to <85 ≥ 85	X		X
	< 70 ≥70	X	X	
Sex	male female	X	X	X
Region	NA, LA, Europe, Asia, Other ⁺	X		X (overall ⁴ only)
Ethnicity	Hispanic/ Latino Not Hispanic/ Latino	X		X (overall ⁴ only)
Race ^s	White Black/ African-American Asian Other including mixed race	X	X	X
BMI (kg/m ²)	<30 ≥30	X	X	
eGFR at baseline	≥90 60 to <90 45 to <60 30 to <45 20 to <30 <20	X		
	≥90 60 to <90 45 to <60 30 to <45 <30	X		X
	≥60 <60	X	X	

Table 6.4: 1 Categories of covariates for displays of baseline characteristics and subgroup analyses (cont.)

Variable	Categorization	Demo- graphics ¹	Subgroups for Efficacy endpoints ²	Safety ³
UACR	UACR (in mg/g): <30 >=30 to <=300 >300	X		
Baseline SBP	< / >= median		X	
Baseline BP	SBP<140 and DBP<90 vs. SBP>= 140 or DBP>=90	X		X (volume depletion AEs and hypotension AEs)
History of Atrial Fibrillation or Atrial Flutter ^{SS}	Yes/ No	X	X	
Baseline LVEF	</>=50	X		
	<50, 50 to <60, >=60	X	X	
History of HHF (in the last 12 months)	Yes / No	X	X	
Time since diagnosis of HF	<= 1 year, 1-5 years, > 5 - 10 years, >10 years	X		
NYHA at baseline	I/II/III/IV	X		
	II vs. III/IV		X	
NT-proBNP	< / >= median (calculated separately for patients with/without history of atrial fibrillation or atrial flutter ^{SS})		X	
Baseline uric acid	Tertiles (calculated separately for males and females)	X	X	
Baseline use of ACE- inhibitor, ARB or ARNi	Yes / No	X#	X	X (renal AEs, volume depletion AEs and hypotension AEs)

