Baseline use of MRA	Yes / No	X#	X	

Table 6.4: 1 Categories of covariates for displays of baseline characteristics and subgroup analyses (cont.)

Variable	Categorization	Demo-graphics ¹	Subgroups for Efficacy endpoints ²	Safety ³
Baseline use of diuretics	Yes / No	X#		X (renal AEs, volume depletion AEs and hypotension AEs)
Baseline use of loop or high-ceiling diuretics	Yes / No	X#		X (renal AEs, volume depletion AEs and hypotension AEs)

¹ The column demographics shows categories shown in the overall demographics.

Demographics are not planned by subgroup.

² Subgroups planned for the primary endpoint, time to cardiovascular (CV) death, time to first HHF, HHF (first and recurrent), renal slope.

³ X means subgroups planned for overall AE summaries, AEs by SOC and PT, SAEs, AEs leading to discontinuation, decreased renal function, UTI, genital infection, volume depletion, hypotension and bone fracture.

⁴ Overall means overall AE summaries, AEs by SOC and PT, SAEs and AEs leading to discontinuation

⁵ Median calculated separately for baseline atrial fibrillation or atrial flutter (determined by ECG) / no baseline atrial fibrillation and atrial flutter (determined by ECG)

⁺ Region categorization: see [Table 9.1.1](#).

[#] part of the presentation of baseline concomitant therapy as outlined in [Section 7.2](#)

[§] Due to low number of patients in certain race categories, estimates for race subgroups may be unstable.

^{§§} history of atrial fibrillation or atrial flutter means atrial fibrillation or atrial flutter reported in any ECG before treatment intake or history of atrial fibrillation or atrial flutter reported as medical history.

Additional subgroup analyses for specific further endpoints are defined in [Section 7.6](#)

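### The eGFR-slope subgroup model leaves out subgroup-by-time and defines no interaction contrast, so the default test of its three-way term mixes effect modification with ordinary slope differences between subgroups

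*SAP*

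**What the plan says.** The main slope model in SAP Section 7.5.1 is a random coefficient model. Its categorical part reads "The model will include the factors treatment, sex, geographical region, and status of DM as fixed effects". Its time-related part is "time and interaction of treatment by time and interaction of eGFR (CKD-EPI)_{cr} at baseline" by time. The last of these was added in the revision: Section 4, item 1, records "an additional fixed effect term of interaction of eGFR" "at baseline (continuous) by time is included".

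For subgroups, the model is extended by "the subgroup if not already part of the model, subgroup by treatment and subgroup by treatment by time", followed by the rule "If the subgroup variable is a categorization of a continuous covariate, this covariate will be dropped from the subgroup model".

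The footnote to Table 6.4:1 lists the endpoints that get efficacy subgroup analyses, ending with "time to first HHF, HHF (first and recurrent), renal slope". Section 6.4 also states that "the subgroup analysis by Diabetes at baseline (diabetic, non-diabetic) is the medically and academically most important subgroup analysis". Section 9.4 adds a five-category baseline eGFR subgroup for the same endpoints, with an interaction p-value from a trend test.

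**The concern.** To ask whether the drug's effect on slope differs between subgroups, the model must first let each subgroup have its own underlying slope. That is the job of subgroup-by-time. Without it, the only term in which slope can vary by subgroup is the three-way term, which is also the natural candidate for the interaction test. A subgroup that simply declines faster in both arms can then look like a subgroup in which the drug works differently.

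At stake is the reading of the exploratory renal-slope subgroup output, including the diabetes subgroup that the SAP ranks highest and the eGFR trend test planned for regional submissions. The plan itself allows slope to depend on a baseline factor, since it added baseline-eGFR-by-time to the main model.

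**Working it through.** **Is the term there under another name?** The condensed notation in Section 4, item 3, is limited to MMRMs. The current MMRM subgroup rule in Section 7.6 replaces treatment-by-visit with the three-way term; the slope text keeps treatment-by-time and adds to it. In the SAP of 21-FEB-2017, the MMRM subgroup model listed subgroup-by-visit, while the slope subgroup model of the same date had no subgroup-by-time. So shorthand does not explain the gap.

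**Set-up.** The SAP gives no figure for this model, so there is none to reproduce. Let d be the treatment effect on slope, the same in both subgroups (no true interaction). Let D be the difference in underlying slope between two equal subgroups, present in both arms.

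**0/1 reference coding (placebo = 0).** The listed terms force one placebo slope on both subgroups, which settles at the midpoint. The empagliflozin slopes stay free and lie D apart. The reported effects are d - D/2 and d + D/2, a spurious interaction of size D. For d = 0.5 and D = 1.0, these are 0.0 and 1.0.

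**SAS class coding.** The three-way term spans the missing one. Design-matrix rank is the same with or without subgroup-by-time (8 for two categories, 12 for three), so the fit and the within-subgroup treatment differences are unchanged (simulation: 0.50 and 0.50 for a true 0.5). The default test of the term, however, has 2(k-1) df: 2 instead of 1, or 4 instead of 2. Half of them belong to subgroup-by-time.

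**Size of the false rejection.**
- From the SAP: N of about 5750 (Section 9.6); on-site visits at weeks 4, 12, 32, 52, 76 and 100 (Table 6.7:1).
- Assumed: 1:1 allocation, complete data to week 100, patient-slope SD 2 to 5, residual SD 6 to 10, test level 0.05, no baseline-eGFR-by-time term.
- Sum of squared deviations of the visit times in years (weeks/52): 2.577.
- Variance of one patient's estimated slope: v = SD² + residual SD²/2.577. Low: 4 + 36/2.577 = 17.97. High: 25 + 100/2.577 = 63.81.
- Noncentrality, class coding (2 df): D²N/(4v).
- Noncentrality, reference coding (1 df, empagliflozin arm only): D²N/(8v).

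For D = 0.5, D²N = 1437.5:

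| | v = 63.81 | v = 17.97 |
|---|---|---|
| Class, noncentrality | 5.63 | 20.0 |
| Class, rejection | 0.555 | 0.985 |
| Reference, noncentrality | 2.82 | 10.0 |
| Reference, rejection | 0.389 | 0.885 |

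For D = 0.25 the ranges are 0.17 to 0.50 (class) and 0.13 to 0.35 (reference). For D = 1.0 they are 0.99 to 1.00 and 0.92 to 1.00. For D = 0 both are 0.05.

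**With subgroup-by-time added.** The three-way term has k-1 df and its rejection rate is 0.050 for every D tried from 0 to 2 (simulation for two categories: 0.048).

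**Trend tests.** A numeric score that enters only through score-by-treatment-by-time, without score-by-time, has the same structure. The five-category eGFR trend test in Section 9.4 is open to the same error.

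**The case against.** The strongest reply is that the SAP never says the default test of the three-way term will be the reported slope interaction. Section 7.5.1 only says that subgroups will be explored. The analyses run in SAS with treatment as a factor, and under class coding a (k-1)-df contrast of the treatment differences in slope is valid in the model exactly as listed. Centred -1/+1 coding with balanced arms also keeps the level at 0.05. This stands as a limit: the error is conditional on coding and on the test chosen. But the plan fixes neither, and the default test is the contaminated one.

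Four stronger readings are tempting and are not supported:
- That the subgroup slope effects will be wrong. This holds only under 0/1 reference coding, which the SAP does not specify.
- That the confirmatory slope result is compromised. The main model does not involve the subgroup terms, and the subgroup analyses sit outside the testing hierarchy.
- That the eGFR 60 split is worst hit because baseline eGFR is dropped there. The SAP says that the covariate is dropped, not that its interaction with time is. If that interaction stays, it absorbs part of the slope difference, and in the other subgroup models it may do so too.
- That diabetic and non-diabetic patients are known to decline at different rates. The SAP gives no such figure. The rejection rates depend on an assumed difference and vanish to 0.05 when it is zero.

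**Conclusion.** The point holds as a defect of specification: the listed terms omit subgroup-by-time, and no slope interaction contrast is defined. If the listed three-way term is tested by default, the p-value does not isolate effect modification. The sizes above illustrate the mechanism and do not forecast this trial: they rest on the assumed slope difference and standard deviations. The consequence is confined to exploratory subgroup and interaction output. That makes it a should-fix.

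**What to change.** In the slope subgroup paragraph of Section 7.5.1, list four terms: subgroup (where not already in the model), subgroup × time, subgroup × treatment, and subgroup × treatment × time. State that the interaction p-value is the (k-1)-df test of the three-way term with subgroup × time in the model. For trend tests, including the five-category eGFR test in Section 9.4, state that score × time is included and that the test has 1 df. Say whether baseline eGFR × time stays in the models for the eGFR subgroups when the continuous covariate is dropped.

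The cost is a few lines of SAP text and one model term. No new data are needed and the main slope analysis does not change.
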